#### **12.7.1 Year 2 – Every 4 Weeks (not required for treatment failure)**

During Year 2, every 4 weeks ( $\pm$  2 weeks), the following procedures will be performed:

- Assessment of Adverse Events and Concomitant Medications (including review of subject diary for bleeding and FVIII use)
- Liver Tests (refer to [Table 9.7.8.3.1](#))
  - LTs may be monitored more or less frequently (and in particular when ALT values are  $\geq 1.5 \times$  ULN or  $>$  ULN &  $>$  2x baseline value) based on discussion between the Medical Monitor and the Investigator and review of subject data, but LTs will be monitored at least twice weekly during periods when a subject's ALT is  $\geq 3 \times$  ULN.
- FVIII Assays
  - FVIII activity level (chromogenic substrate FVIII assay)
  - FVIII activity level (one-stage clotting FVIII assay)
  - FVIII coagulation activity exploratory assay
  - Bethesda assay (with Nijmegen modification) for FVIII inhibitor level
  - FVIII protein assay
- PCR of vector DNA in blood, saliva, urine, semen, and stools (if required)
  - Sample testing during Year 2 is not required if at least 3 consecutive samples are negative during the Post-Infusion Follow-Up period in Weeks 1-52. Subjects who have not had 3 consecutive negative semen samples by Week 52 should continue to have PCR testing of semen every 4 weeks during Years 2 until 3 consecutive negative samples are documented (or upon consultation between the Investigator and Medical Monitor).
  - Subjects who meet the definition of treatment failure and wish to follow an abbreviated schedule but who have not cleared vector shedding from all fluids must still provide samples for assessment every 4 weeks during Year 2 until vector shedding has cleared. Such subjects may provide samples on the designated study visit dates either at the sites or through use of a MN professional.

## 12.7.2 Years 3-5 – Every 6 Weeks (not required for treatment failure)

During Years 3-5, every 6 weeks ( $\pm$  2 weeks), the following procedures will be performed:

- Assessment of Adverse Events and Concomitant Medications (including review of subject diary for bleeding and FVIII use)
- Liver Tests (refer to [Table 9.7.8.3.1](#))
  - LTs may be monitored more or less frequently (and in particular when ALT values are  $\geq 1.5 \times$  ULN or  $>$  ULN &  $>$  2x baseline value) based on discussion between the Medical Monitor and the Investigator and review of subject data, but LTs will be monitored at least twice weekly during periods when a subject's ALT is  $\geq 3 \times$  ULN.
- FVIII Assays
  - FVIII activity level (chromogenic substrate FVIII assay)
  - FVIII activity level (one-stage clotting FVIII assay)
  - FVIII coagulation activity exploratory assay
  - Bethesda assay (with Nijmegen modification) for FVIII inhibitor level
    - If a subject tests positive in the Bethesda assay (with Nijmegen modification) during Years 3-5, a fresh sample should be collected within 4 weeks of the initial visit that had a positive result.
  - FVIII protein assay
- PCR of vector DNA in blood, saliva, urine, semen, and stools (if required)
  - Sample testing during Years 3-5 is not required if at least 3 consecutive samples are clear by the end of Year 2. Subjects who have not had 3 consecutive negative semen samples by the end of Year 2 should continue to have PCR testing of semen every 6 weeks during Years 3-5 until 3 consecutive negative samples are documented (or upon consultation between the Investigator and Medical Monitor).
  - Subjects who meet the definition of treatment failure and wish to follow an abbreviated schedule but who have not cleared vector shedding from all fluids must still provide samples for assessment every 6 weeks during Years 3-5 until vector shedding has cleared. Such subjects may provide samples on the designated study visit dates either at the sites or through use of a MN professional.

### 12.7.3 Years 2-5 – Every 12 Weeks and End of Year Visits (required for all subjects)

During Years 2-5, subjects will be asked to return to the study site for visits at the following study weeks ( $\pm 2$  weeks):

- Year 2 – Week 64, Week 76, Week 88, Week 104
- Year 3 – Week 116, Week 128, Week 140, Week 156
- Year 4 – Week 168, Week 180, Week 192, Week 208
- Year 5 – Week 220, Week 232, Week 244, Week 260

For each of these years, the last study visit listed (Week 104, Week 156, Week 208, and Week 260) will serve as an End of Year visit. The every 12 week and End of Year visits may not be performed remotely by MN services.

At the every 12 week and End of Year visits, the following procedures will be performed:

- Physical examination
  - Complete physical examination will be performed at the End of Year visits; brief physical examination may be performed at other visits.
- Weight (at Week 76, Week 128, Week 180, Week 232, and End of Year visits only)
- Assessment of Adverse Events and Concomitant Medications (including review of subject diary for bleeding and FVIII use)
- Liver Tests (refer to [Table 9.7.8.3.1](#))
  - LTs may be monitored more or less frequently (and in particular when ALT values are  $\geq 1.5$ x ULN or  $>$  ULN &  $>$  2x baseline value) based on discussion between the Medical Monitor and the Investigator and review of subject data, but LTs will be monitored at least twice weekly during periods when a subject's ALT is  $\geq 3$ x ULN.
- FVIII Assays
  - FVIII activity level (chromogenic substrate FVIII assay)
  - FVIII activity level (one-stage clotting FVIII assay)
  - FVIII coagulation activity exploratory assay
  - Bethesda assay (with Nijmegen modification) for FVIII inhibitor level
  - FVIII protein assay
- Blood chemistry, hematology, and coagulation tests (refer to [Table 9.7.8.2.1](#)) (at Week 76, Week 128, Week 180, Week 232, and End of Year visits only)

- Urine Tests (refer to [Table 9.7.8.2.1](#)) (at Week 76, Week 128, Week 180, Week 232, and End of Year visits only)
- Vital Signs
- AAV5 TAb Assay
- AAV5 TI Assay
- FVIII antibody titer
- Haemo-QoL-A assessment (at Week 76, Week 128, Week 180, Week 232, and End of Year visits only)
- EQ-5D-5L (at Week 76, Week 128, Week 180, Week 232, and End of Year visits only)
- HAL (at Week 76, Week 128, Week 180, Week 232, and End of Year visits only)
- WPAI+CIQ:HS (at Week 76, Week 128, Week 180, Week 232, and End of Year visits only)
- PROBE (at Week 76, Week 128, Week 180, Week 232, and End of Year visits only)
- Exploratory biomarker assessments
- PBMC collection
- VWF:Ag
- TGA Assay
- PCR of vector DNA in blood, saliva, urine, semen, and stools (if required)
  - Sample testing during Years 2-5 is not required if at least 3 consecutive samples are negative during the Post-Infusion Follow-Up period in Weeks 1-52. Subjects who have not had 3 consecutive negative semen samples by Week 52 should continue to have PCR testing of semen every 4 weeks (during Year 2) or every 6 weeks (during Years 3-5) until 3 consecutive negative samples are documented (or upon consultation between the Investigator and Medical Monitor).

## 12.8 Early Termination Visit

The Early Termination visit will occur on the date the subject withdraws from the study, even if the date does not correspond to a protocol-specific visit.

If a subject leaves the study prior to the Week 260 visit, the subject will be asked to return to the study site and complete an Early Termination visit. At the Early Termination visit, as many of the following assessments as possible should be done:

- Physical examination

- Weight
- Assessment of Adverse Events and Concomitant Medications (including review of subject diary for bleeding and FVIII use)
- Vital Signs
- Blood chemistry, hematology, and coagulation tests (refer to [Table 9.7.8.2.1](#))
- Urine Tests (refer to [Table 9.7.8.2.1](#))
- Liver Tests (refer to [Table 9.7.8.3.1](#))
- FVIII Assays
  - FVIII activity level (chromogenic substrate FVIII assay)
  - FVIII activity level (one-stage clotting FVIII assay)
  - FVIII coagulation activity exploratory assay
  - Bethesda assay (with Nijmegen modification) for FVIII inhibitor level
  - FVIII protein assay
- AAV5 TAb Assay
- AAV5 TI Assay
- FVIII antibody titer
- Exploratory biomarker assessments
- PBMC collection
- VWF:Ag
- TGA Assay
- PCR of vector DNA in blood, saliva, urine, semen, and stools
  - Sample testing at the ETV is not required if at least 3 consecutive samples were clear during the Post-Infusion Follow-Up period.
- Haemo-QoL-A assessment
- EQ-5D-5L
- HAL
- WPAI+CIQ:HS
- PROBE

**12.9 End of Study**

The study will end after the last subject yet to complete the last Long-Term Follow-Up visit (Week 260) does so, has transferred to another BMN 270 study, is withdrawn from the study, or discontinues from the study. BioMarin reserves the right to discontinue the study any time for clinical or administrative reasons and to discontinue participation of an individual Investigator or site for clinical or administrative reasons, including, but not limited to, poor enrollment or noncompliance with procedures of the protocol or GCP. In addition, the study may be terminated if, in the opinion of BioMarin, the safety of the study subjects may be compromised.

**13 DATA QUALITY ASSURANCE**

BioMarin personnel or designees will visit the study site prior to initiation of the study to review with the site personnel information about the IP, protocol and other regulatory document requirements, source document requirements, eCRFs, monitoring requirements, and procedures for reporting AEs, including SAEs.

At visits during and after the study, a CRA will monitor the site for compliance with regulatory documentation, with a focus on accurate and complete recording of data on eCRFs from source documents, adherence to protocol, randomization (if applicable), SAE reporting and drug accountability records.

Data quality control and analysis will be performed by BioMarin or a designee, based on a predefined analysis plan.

## 14 STATISTICAL METHODS AND DETERMINATION OF SAMPLE SIZE

### 14.1 Statistical and Analytical Plans

The statistical analysis plan (SAP) will provide additional details on the planned statistical analysis. Unless otherwise stated, all analyses will be performed using SAS.

#### 14.1.1 Interim Analyses

An interim analysis is planned after approximately 20 treated HIV-negative subjects have completed the Week 26 visit (or have discontinued study participation prior to Week 26). Data will be reviewed by the DMC, based on the SAP, and a formal recommendation will be made whether to continue the study as designed.

The primary efficacy endpoint for the interim analysis involves hFVIII activity, as measured by chromogenic substrate assay, achieved post-BMN 270 infusion.

The secondary and tertiary endpoints will be summarized descriptively at the interim (Week 26) analysis.

The details of the interim analysis, including the control of Type I error rate, will be specified in the SAP.

#### 14.1.2 Procedures for Accounting for Missing, Unused and Spurious Data

Because the completeness of the data affects the integrity and accuracy of the final study analysis, every effort should be made to ensure complete, accurate, and timely data collection and, therefore, avoid missing data.

Sensitivity analyses will be conducted to assess the impact of missing data on the primary efficacy endpoint analysis. Additional details regarding the handling of missing data will be provided in the SAP.

### 14.2 Primary Efficacy Endpoint

For the primary efficacy endpoint at Week 52 (ie, the change in the hFVIII activity during Weeks 49-52 post-BMN 270 infusion from baseline, as measured by chromogenic substrate

assay), a one-sample t-test will be used to test the null hypothesis that the change is 0 or less against the alternative hypothesis that the change is greater than 0. Descriptive summaries of the proportions of subjects whose FVIII activity during Weeks 49-52 is greater than or equal to select thresholds, such as 15, 25 and 30 IU/dL, and the confidence intervals of the proportions will also be provided.

For a subject with a missing value of the primary endpoint, the median value in the subject's last 4-week window containing a valid observation will be used. Additional analyses will be conducted to examine the sensitivity of the results to the handling of missing data, including analysis using observed cases, and a mixed model for repeated measures (MMRM) approach. Further detail will be provided in the SAP.

The analyses for the primary endpoint will be performed using the analysis populations as defined in Section 14.8.

#### 14.3 Secondary Efficacy Endpoints

The primary analyses for the secondary endpoints will be performed on the 35 subjects in the mITT population who will be followed up for approximately 6 months in the non-interventional study 270-902 prior to their enrollment in 270-302. The baseline values will be derived from the prospectively collected data in 270-902.

For the first secondary efficacy endpoint at Week 52 (ie, the change in the annualized utilization (IU/kg) of exogenous FVIII replacement therapy during Weeks 5-52 post-BMN 270 infusion from baseline), a one-sample t-test will be performed to test the null hypothesis that the change is 0 or greater against the alternative hypothesis that the change is less than 0.

For the second secondary efficacy endpoint at Week 52 (ie, the change in ABR, annualized bleeding rate, during Weeks 5-52 post-BMN 270 infusion from baseline), a one-sample t-test will be performed to test for non-inferiority of BMN 270 against FVIII prophylaxis (ie, the baseline ABR calculated using subjects' data collected as part of 270-902) using a non-inferiority margin of 3.5, ie, to test the null hypothesis that the change is 3.5 or greater against the alternative hypothesis that the change is less than 3.5. If non-inferiority is demonstrated, the test for superiority of BMN 270 against FVIII prophylaxis will be performed.

A sensitivity analysis is planned to analyze ABR using a generalized linear mixed model assuming negative binomial as the underlying distribution. The model will include period (pre- to post-BMN 270 infusion) as the only factor. The actual number of bleeding episodes

---

will be used as the independent variable with the time period adjustment (animalization) being implemented as the offset.

To assess the impact of missing data, analyses using observed case are planned as sensitivity analyses for the secondary endpoints. Multiple imputation methods may also be performed.

The primary and secondary efficacy hypotheses will be tested hierarchically according to the order described above. Multiple comparison procedures are described in greater detail in the SAP.

#### **14.4 Immunogenicity**

Analysis of total and neutralizing antibody response and other immunological parameters will be primarily descriptive and involve both inter-subject and intra-subject comparisons.

#### **14.5 Pharmacodynamic Analyses**

Plasma FVIII protein concentrations and FVIII activities determined over the course of the study will primarily be evaluated and summarized with descriptive statistical measures (eg, mean, standard deviation, CV%, min, median, max).

#### **14.6 Safety Analysis**

The Medical Dictionary for Regulatory Activities terminology (MedDRA) will be used by the Sponsor to assign system organ class and preferred term classification to events and diseases, based on the original terms entered on the eCRF.

All AEs will be coded using the current version of MedDRA. The incidence of AEs will be summarized by system organ class, preferred term, relationship to study drug, and severity. A by-subject listing will be provided for those subjects who experience a serious AE (SAE), including death, or experience an AE associated with early withdrawal from the study or study drug.

Clinical laboratory data will be summarized by the type of laboratory test. For each clinical laboratory test, descriptive statistics will be provided on Baseline as well as all subsequent visits. Descriptive statistics for physical examination results and vital signs will also be provided.

Detailed statistical methods will be provided in the SAP.

#### 14.7 Determination of Sample Size

Approximately 40 subjects may be dosed in the study. The sample size for this study is based on clinical and statistical considerations in order to provide sufficient data to assess both safety and efficacy of BMN 270.

For the primary endpoint, a sample size of 40 will provide at least 90% power to demonstrate that the change in hFVIII activity at Weeks 49-52 from baseline is greater than 0, assuming an effect size of 0.6, using a one-sample t-test with a 2-sided significance level of 0.05.

For the secondary endpoints, the analysis will be performed utilizing exogenous FVIII use and bleeding episode data from the 35 subjects whose baseline data will be prospectively collected for approximately 6 months in the non-interventional study 270-902, prior to their enrollment in 270-302. An analytic sample size of 35 will provide at least 90% power to demonstrate that the change in the annualized utilization (IU/kg) of exogenous FVIII replacement therapy during Week 5 to Week 52 post-BMN 270 infusion from the baseline is less than 0, assuming an effect size of 0.6, using one-sample t-test with a 2-sided significance level of 0.025.

For the analytic sample size calculation of the second secondary endpoint, ABR, it is assumed that the pre- and post-BMN 270 infusion population mean ABRs are 3.5 and 1 respectively, and the distribution of ABRs is negative binomial distribution with a dispersion parameter of 2.2.

Under this assumption, an analytic sample size of 35 will also have at least 95% power to demonstrate that the change in the annualized number of bleeding episodes requiring exogenous FVIII replacement treatment (ABR) during Week 5 to Week 52 of the study post-BMN 270 infusion from the baseline ABR is less than 3.5 (non-inferiority margin), using a one-sample t-test with a 2-sided significance level of 0.05.

Overall, a sample size of 40 will have greater than 80% power for testing the primary and secondary efficacy endpoints hierarchically at the final analysis with a 2-sided significance level of 0.05.

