
For the secondary endpoints, the analyses will be performed utilizing exogenous FVIII use and bleeding episode data from the 35 subjects whose baseline data will be prospectively collected for approximately 6 months in the non-interventional study 270-902, prior to their enrollment in 270-302. An analytic sample size of 35 will provide at least 90% power to demonstrate that the change in the annualized utilization (IU/kg) of exogenous FVIII replacement therapy during Week 5 to Week 52 post-BMN 270 infusion from baseline is less than 0, assuming an effect size of 0.6, using a one-sample t-test with a 2-sided significance level of 0.05.
 
An analytic sample size of 35 will also have at least 95% power to demonstrate that the change in the annualized number of bleeding episodes requiring exogenous FVIII replacement treatment (ABR) during Week 5 to Week 52 of the study post-BMN 270 infusion from the baseline ABR is less than 3.5 (non-inferiority margin), assuming the pre- and post-BMN 270 infusion population mean ABRs are 3.5 and 1 respectively, using a one-sample t-test with a 2-sided significance level of 0.05.
 
Overall, a sample size of 40 will have greater than 80% power for testing the primary and secondary efficacy endpoints hierarchically at the final analysis with a 2-sided significance level of 0.025.
		

Analysis Population
 
The intention-to-treat (ITT) population is defined as all subjects who receive BMN 270 infusion, and the modified intention-to-treat (mITT) population is defined as subjects who receive BMN 270 infusion and are HIV-negative. The mITT population will be used for the primary efficacy analysis, and the ITT population will be used for the supportive efficacy analysis. The ITT population will also be used for the safety analysis.
		

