
For the first secondary efficacy endpoint at Week 52 (ie, the change in the annualized utilization (IU/kg) of exogenous FVIII replacement therapy during Weeks 5-52 post-BMN 270 infusion from baseline), a one-sample t-test will be performed to test the null hypothesis that the change is 0 or greater against the alternative hypothesis that the change is less than 0.
 
For the second secondary efficacy endpoint at Week 52 (ie, the change in the annualized number of bleeding episodes requiring exogenous FVIII replacement treatment during Weeks 5-52 post-BMN 270 infusion from baseline), a one-sample t-test will be performed to test for non-inferiority of BMN 270 against FVIII prophylaxis (ie, the baseline ABR calculated using subjects' data collected in 270-902) using a margin of 3.5, ie, to test the null hypothesis that the change is 3.5 or greater against the alternative hypothesis that the change is less than 3.5. If non-inferiority is demonstrated, the test for superiority of BMN 270 against FVIII prophylaxis will be performed.
 
The primary efficacy endpoint and secondary efficacy endpoints will be tested hierarchically at the final analysis at Week 52 according to the order described above.
 
An interim analysis is planned after approximately 20 treated HIV-negative subjects have completed the Week 26 visit (or have discontinued participation prior to Week 26). The primary efficacy endpoint for the interim analysis involves hFVIII activity, as measured by chromogenic substrate assay, achieved post-BMN 270 infusion, as detailed in the Statistical Analysis Plan (SAP).
 
Adjustment for multiplicity of the interim analysis at Week 26 and the final analysis at Week 52 will be described in the SAP (regardless of the interim analysis results, the study is planned to continue upon the DMC's recommendation, and the final analysis will be performed at Week 52). At the final analysis at Week 52, the secondary efficacy endpoints will be tested hierarchically.
 
The secondary efficacy endpoints at the interim analysis (Week 26) will be summarized descriptively.
 
The tertiary endpoints will be analyzed at the interim (Week 26) and final (Week 52) analyses, irrespective of the aforementioned hierarchical testing.
 
Details of the interim analysis, including the control of Type I error rate, will be specified in the SAP.
 
Analysis of safety endpoints will be primarily descriptive. The incidence of AEs will be summarized by system organ class, preferred term, relationship to study drug, seriousness, and severity. Clinical laboratory test values, vital signs, vector shedding and immune response parameters will be summarized descriptively by visit.
		

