In order to support a filing of application for marketing approval of BMN 270 based on Study 270-301 interim data, an additional interim analysis of Study 270-302, which was covered in interim analysis plan version 1 (dated 24 April 2019), was implemented around the same time of the Study 270-301 interim analysis to provide supportive baseline and safety data.

In order to provide ancillary baseline, efficacy and safety data to support filing of application for marketing approval of BMN 270 based on Study 270-301 Year 1 data, a second interim analysis is planned; this analysis plan is for this second interim analysis. Additional interim analyses of Study 270-302 may also be performed depending on the amount of additional data accumulated when necessary

INTERIM ANALYSIS POPULATIONS

As mentioned above, in order to support a filing of application for marketing approval of BMN 270 based on Study 270-301 Year 1 data, an interim analysis of Study 270-302 is planned to provide supportive baseline, efficacy and safety data. The following are populations for this interim analysis.

All Screened Subjects: all screened subjects in the study.

All Enrolled Subjects: all enrolled subjects in the study.

Intention-to-treat (ITT) Population: all enrolled, treated subjects in the study.

Screening status and screen failure reasons will be listed for all screened subjects. [REDACTED]

ENDPOINTS AND ANALYSES:

Primary and secondary efficacy endpoints and analyses:

Since only one subject was enrolled in the study, no summary tables will be generated and only [REDACTED]

Safety endpoints and analyses:

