4 INTRODUCTION

This document describes the statistical methods to be implemented in the interim analysis of data collected under clinical study protocol 270-302, “A Phase 3 Open-Label, Single-Arm Study To Evaluate The Efficacy and Safety of BMN 270, an Adeno-Associated Virus Vector–Mediated Gene Transfer of Human Factor VIII at a dose of 4E13 vg/kg in Hemophilia A Patients with Residual FVIII Levels \leq 1 IU/dL Receiving Prophylactic FVIII Infusions” (Global Amendment 4, 09 November 2018). The Interim SAP contains definitions of analysis populations, derived variables, and statistical methods for the analyses of baseline, efficacy and safety data in order to support a filing of application for marketing approval of BMN 270 based on Study 270-301 Year 1 data.

The objectives of the study are to assess the efficacy of BMN 270 on FVIII activity, usage of exogenous FVIII replacement therapy, and number of bleeding episodes; patient-reported outcomes (PROs); and to evaluate the long-term safety of BMN 270 following intravenous infusion.

This is a Phase 3, single-arm, open-label study in hemophilia A (HA) patients with residual FVIII levels \leq 1 IU/dL treated continuously with prophylactic exogenous FVIII for a minimum of one year prior to enrollment. It was planned that subjects would be enrolled at approximately 40 sites worldwide. Approximately 40 adult subjects with severe HA were planned to receive a 4E13 vg/kg dose of BMN 270 as a single intravenous infusion:

- Directly enrolled subjects: The first approximately 5 subjects will enroll in the study with at least 12 months of well-documented high-quality historical data concerning previous bleeding episodes and exogenous FVIII usage.
- Study 270-902 rollover subjects: The rest, approximately 35 subjects, will enroll in the study after having completed approximately 6 months’ participation in the BioMarin-sponsored non-interventional study 270-902, in which bleeding and FVIII use data prior to gene therapy will be prospectively collected.

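### Protocol synopsis and Section 14.7 print different 2-sided alphas for FVIII use and for overall power; at the 0.025 in Section 14.7, FVIII-use power is 88.0%, below the stated 90%

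*Protocol*

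**What the plan says.** The protocol makes four power statements, once in the synopsis (Statistical Methods, Sample Size) and again in Section 14.7. Two agree: the primary endpoint and ABR non-inferiority are at 2-sided 0.05 in both places. Two do not:

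- **FVIII use (first secondary endpoint), n = 35, at least 90% power.** The synopsis has "assuming an effect size of 0.6, using a one-sample t-test with a 2-sided significance level of 0.05". Section 14.7 has "assuming an effect size of 0.6, using one-sample t-test with a 2-sided significance level of 0.025".
- **Overall hierarchical power, n = 40, above 80%.** The synopsis refers to testing the "primary and secondary efficacy endpoints hierarchically at the final analysis with a 2-sided significance level of 0.025". Section 14.7 refers to the "primary and secondary efficacy endpoints hierarchically at the final analysis with a 2-sided significance level of 0.05".

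Sections 14.2 and 14.3 and the synopsis analysis text describe the tests without giving an alpha. They pass multiplicity on: "Adjustment for multiplicity of the interim analysis at Week 26 and the final analysis at Week 52 will be described in the SAP" (synopsis) and "Multiple comparison procedures are described in greater detail in the SAP" (Section 14.3). The SAP supplied is an interim plan. Its Introduction opens: "This document describes the statistical methods to be implemented in the interim analysis of data collected under clinical study protocol 270-302".

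**The concern.** In each mismatched pair the sample size, the stated power and (for FVIII use) the effect size are the same; only alpha changes. The two mismatches run in opposite directions, so neither place is simply the stricter version, and neither is consistent within itself. Section 14.7 powers FVIII use at 0.025 inside a sequence that it says runs at 0.05. The synopsis powers each component at 0.05 inside a sequence that it says runs at 0.025. The amendment table in Section 25 lists no change to these paragraphs, so both sets of figures are current text.

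Two things are at stake: which significance level governs the final hierarchical sequence, and whether the power claimed for the first secondary endpoint is true.

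**Working it through.** **Inputs.** Effect size 0.6, one-sample t-test, n = 40 (primary) and n = 35 (FVIII use), 2-sided alpha 0.05 or 0.025, all from the synopsis and Section 14.7. No dropout inflation applies, since 35 is already called the analytic sample size.

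**Formula.** Power = P(T > c), where T is noncentral t with n − 1 degrees of freedom and noncentrality 0.6·√n, and c is the central t quantile at 1 − alpha/2.

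**FVIII use, n = 35.** Noncentrality = 0.6 × √35 = 3.550.

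| 2-sided alpha | Critical t (34 df) | Power, t-test | Power, normal approximation |
|---|---|---|---|
| 0.05 (synopsis) | 2.032 | 93.2% | 94.4% |
| 0.025 (Section 14.7) | 2.345 | 88.0% | 90.5% |

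The stated bound of 90% is met at 0.05. At 0.025 the named test misses it by 90.0 − 88.0 = 2.0 points. Only the normal approximation, Φ(3.550 − 2.241) = 90.5%, clears it, and that is not the test named. At 0.025, n = 37 gives 89.96% and n = 38 gives 90.8%, so the bound would need 38 analysed subjects.

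**Primary, n = 40.** Noncentrality = 0.6 × √40 = 3.795. Power is 95.9% at 0.05 and 92.4% at 0.025, so at least 90% holds either way.

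**ABR non-inferiority, n = 35.** Simulated with 100,000 runs: means 3.5 and 1, margin 3.5, negative binomial with dispersion 2.2. One-year counts and independent pre- and post-infusion counts are assumptions. Power is about 100% at either alpha, whether 2.2 is read as k in variance = μ + kμ² or as 1/k.

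**Overall power through ABR non-inferiority.** Taking the endpoints as independent and multiplying:

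- both tests at 0.05: 0.9591 × 0.9316 × 1.00 = 89.3%
- both tests at 0.025: 0.9236 × 0.8801 × 1.00 = 81.3%
- component alphas exactly as in Section 14.7 (primary 0.05, FVIII use 0.025): 0.9591 × 0.8801 × 1.00 = 84.4%

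All exceed 80%. The documents give no correlation between the FVIII-activity and FVIII-use changes. An assumed correlation of 0.3 to 0.6 raises the figures to 89.8–90.6% at 0.05 and 82.3–83.7% at 0.025. None of these figures includes the ABR superiority step.

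**The case against.** The case for treating this as minor has real content.

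- **It may be a misprint.** Six of the eight printed alphas are 0.05, including the synopsis version of the FVIII-use sentence. If 0.025 in Section 14.7 is a slip, no power figure is wrong. That is possible, but it leaves the 0.025 in the synopsis overall statement unexplained, and the documents do not identify either figure as the slip. The 88.0% therefore stands only conditionally, on 0.025 being meant.
- **The shortfall is small.** About 2 points, and a normal approximation passes. True; the firm error is the contradictory alpha, and the shortfall is its consequence.
- **The governing text may lie elsewhere.** The interim SAP's contents list a summary of changes to the study SAP, so a separate study SAP appears to exist. The protocol's reference list also includes a paper on the fallback procedure, an alpha-allocation method. A single alpha may well have been fixed in a document not supplied. That would settle the intended value but would not make the protocol's two places agree.
- **Nothing will be tested.** The SAP synopsis says: "Since only one subject was enrolled in the study, no summary tables will be generated". This limits the consequence, not the correctness of the point.
- **Overall power is not fully confirmed.** The sequence continues to ABR superiority after non-inferiority, and the protocol does not say whether its figure of above 80% includes that step. Under the same simulation assumptions, superiority power is about 80% at 0.05 and 66% at 0.025 if variance = μ + 2.2μ², but above 99% at both alphas under the other reading of the dispersion. This objection stands as a limit on the check: the overall claim is supported only through non-inferiority.

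**Conclusion.** The concern holds. Two of the four power statements carry contradictory 2-sided alphas in current protocol text, and nothing in the supplied documents resolves them. As printed in Section 14.7, the FVIII-use claim of at least 90% is not met: the named t-test has 88.0% power. As printed in the synopsis, it is met, at 93.2%. These two figures need only the protocol's own n, effect size and test. No other power claim changes from true to false with the choice of alpha, given the ABR simulation assumptions, independence for the overall figure, and exclusion of the superiority step.

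It should be corrected, but its reach is limited. With one subject enrolled and only listings planned, no confirmatory test depends on it. What it affects is the accuracy of the protocol record and of any report that repeats the sample-size basis.

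**What to change.** State one 2-sided alpha for the final hierarchical sequence and print it identically in the synopsis, in Section 14.7 and in whichever SAP governs the final analysis. The sponsor must say which value was intended.

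- **If 0.05:** correct the FVIII-use alpha in Section 14.7 and the overall-power alpha in the synopsis. No power figure changes.
- **If 0.025:** use it in all four statements and restate FVIII-use power as about 88%. The primary and ABR non-inferiority figures stand, as does the overall figure as far as it was checked, through non-inferiority.

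The cost is wording only, with at most one power figure reduced.
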